The secondary objective is to compare the effectiveness of Cognitive Processing Therapy and Accelerated Resolution Therapy in reducing depression symptom severity.

C. Tertiary Objective

The tertiary objective is to examine whether treatment effectiveness is reduced when patient preference for treatment is incongruent with their random assignment.

D. Exploratory Analyses

Exploratory analyses will be performed to examine whether demographic (e.g., sex, age, Veteran/Non-Veteran status) and other clinically-relevant variables (e.g., sleep quality, anger, pain, health care utilization) predict differential response and/or drop-out across treatment condition.

III. Study Design

This study will examine the effectiveness of Cognitive Processing Therapy (CPT) as compared to Accelerated Resolution Therapy (ART) and a Wait list (WL) control using a Randomized, Cross-Over Design with blinded assessment. 280 participants will be randomly assigned to receive ART, CPT or WL condition. Upon completion of the WL condition after 7 weeks, participants will be re-randomized to ART or CPT.

The primary outcome is improvement in PTSD symptom severity as measured by change on the Clinician-Administered PTSD Scale for DSM-IV or DSM-5 (CAPS-IV/ CAPS-5) after treatment. This primary outcome measure will be administered by post-doctoral fellows in psychology who will remain blinded to treatment condition. The

CAPS-IV and CAPS-5 will be administered at pre- and post-treatment, and 3-month and 1-year follow-up visits.

A. Study Population

Participants will be 280 male and female Veterans and civilians who meet criteria for PTSD, or subthreshold PTSD, due to any Criterion A traumatic event. Subthreshold PTSD occurs when a patient has a Criterion A traumatic event, and endorses symptoms in each of the PTSD Diagnostic Criteria (B-E), but falls below the number and/or severity of total Criterion requirements to meet criteria for a PTSD diagnosis. Inclusion and exclusion criteria and recruitment are described in Section IV.

1. Rationale for Inclusion of Non-Veteran participants

Civilians will be included in this study as they have different Criterion A traumatic events (e.g., non-combat). It is imperative to the primary study objective to assess the comparative effectiveness of CPT and ART across a variety of trauma(s).

B. Study Treatment Conditions

1. Treatment Conditions

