* Prior to the phone screen, participants will be asked to identify how they learned about the study and which site (UC or VA) they were referred from. Veteran participants may be seen at the Cincinnati VAMC or the UC Health Stress Center depending on their associated site. All civilian participants will be seen at the UC Health Stress Center.

D. Outcome Measures

The primary outcome is improvement in PTSD symptom severity as measured by clinically significant change on the Clinician-Administered PTSD Scale for DSM-IV or DSM-5 (CAPS-IV/CAPS-5).

A complete description of all of the outcome measures is in Appendix B.

E. Sample Size and Planned Statistical Analyses

1. Planned Statistical Analyses

The primary objective is to compare the effectiveness of CPT and ART in reducing the primary outcome -- PTSD symptom severity -- for Veteran and civilian patients with PTSD. We predict that CPT will be significantly superior to WL (and potentially superior to ART) in reducing PTSD symptoms post-treatment. To test this hypothesis we will use a 3 (Group: CPT, ART, WL) x 4 (Time: Baseline, Post-treatment) mixed-model ANCOVA covarying for baseline PTSD ratings. A significant omnibus interaction, and lower-order interactions, in the hypothesized direction will confirm this hypothesis.

The secondary objective is to compare the effectiveness of CPT and ART in reducing depression symptom severity. We predict that CPT will be superior to WL (and potentially ART) in reducing depression symptoms post-treatment. We will test this hypothesis with a mixed-model ANCOVA following the same analysis plan as for the primary objective.

The tertiary objective is to examine whether treatment effectiveness is reduced when patient preference for treatment is incongruent with their random assignment as we predict. To test this hypothesis, we will first categorize participants to a dichotomized preference group based on self-report. We will then perform a 2 (Group: Preferred Therapy, Non-preferred Therapy) x 4 (Time: Baseline, Post-Treatment, 3 Month, 1 Year) mixed-model ANCOVA covarying for baseline PTSD for both the primary (PTSD) and secondary (depression) outcome variables. A significant omnibus interaction, and lower-order interactions, in the hypothesized direction will confirm this hypothesis. Additionally, the primary and secondary analyses will be rerun covarying for preference to examine this variable's differential influence on CPT and ART outcomes.

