Exploratory analyses will be performed to examine whether demographic and clinical variables differentially predict response and drop-out across treatment condition. Considering the exploratory nature of these analyses we make no predictions. However, we will use hierarchical multiple regression to examine the influence of demographics independent of the influence of clinical factors in predicting response (i.e., 50% symptom reduction) and drop out for each treatment. Based on the sample size estimate below, we will recruit a sample sufficient to include up to 24 predictors within these analyses – a more than sufficient number.

2. Sample Size Estimates

In order to estimate sample size, we used means and SDs from pilot data, prior studies from other groups (Frost et al., 2014; Kip et al., 2012; 2014) and a previously published study from our group (Suris et al., 2013) to determine the expected effect size (ES) for differences in PTSD symptoms across pre- and post-treatment (i.e. time). We also calculated treatment differences at the post-treatment time point only. We employed the ES metric delta (Δ) for mean time differences and Cohen's d for mean treatment differences. According to Cohen (1990), an ES $d = 0.2$ is considered small, 0.5 medium, and 0.8 large for behavioral research. Effect sizes within the large range are clinically relevant for behavioral research and even medium effect sizes should be “visible to the naked eye of a careful observer (Cohen, 1990).” Sample size estimates were then made using G*Power version 3.1 (Franz Faul, University of Keil, Germany). Using G*Power, we also estimated the a priori sample size required to identify the repeated-measures ANOVA interaction terms to be tested in the primary and secondary analyses.

ESs were large for active treatment differences across pre- and post-treatment times ($d = 1.04$ for CAPS reduction with CPT; $d = 2.02$ for PCL reduction in civilians with ART; $d = 1.28$ for PCL reduction in military with ART). To detect similarly large differences ($d_s > 0.8$) in PTSD severity means over time at $\alpha = 0.05$, power = 0.95 (to be conservative since there should be considerable power for these analyses), two-tailed in the proposed study would require at least a total $N = 32$ ($n = 16$ for each active treatment). A total sample size of $N = 152$ ($n = 76$ per active treatment condition) would be required

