to identify PTSD symptom reductions over pre-and post-treatment in the WL condition considering the medium ES.

ES was small for active treatment difference between CPT and PCT symptoms post-treatment ($d = 0.16$). No data directly comparing CPT and ART are available in the extant literature. To detect a similarly small difference ($d_s < 0.2$) in PTSD severity means post-treatment with $\alpha = 0.05$, power = 0.80, two-tailed in the proposed study would require at least a total $N = 706$ ($n = 353$ for each active treatment). Therefore, the proposed $N = 240$ would be insufficient to identify statistically significant differences between CPT and ACT post-treatment if we assume a similarly small effect size. The extant literature does not provide ES estimates between CPT vs. WL and ART vs. WL, but these ESs would be expected to be considerably larger than the CPT vs. PCT estimate.

In the absence of prior WL data with which to estimate ES, and considering that we intend to test interaction effects primarily, we estimate the necessary sample size to detect statistically significant Time x Treatment interactions across the entire power and ES range. Results indicate that for the primary analysis we will have sufficient power to detect even small effects with a total sample size = 246 ($n = 123$ per active treatment condition). For the secondary analysis we will have sufficient power to detect even small effects with a total sample size = 138 ($n = 69$ per active treatment condition).

It should be noted that the above calculations are based on simple contrasts between means and hypothetical power functions for the interaction term in repeated measures ANOVA, none of which include covariates. **These estimates are conservative in that inclusion of covariates, as expected in the final analysis, generally increases power and we intend to over-sample minimally to accommodate participant attrition, further assuring adequate power. *The total sample, then, will be N = 240, split equally between the two active treatments.*** This estimate, based primarily on repeated measure ANOVA, is very conservative as it provides a sufficient sample size to detect even small interaction effects. If needed, we propose oversampling by up to 40 participants to account for drop-outs from assessment or to bolster marginal effects.

F. Random Assignment:

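### The stated capacity for up to 24 predictors is not supported for yes/no outcomes analysed within each treatment, and no term is specified that tests differential prediction

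*Combined protocol and SAP*

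**What the plan says.** Section II.D sets the exploratory aim: whether demographic and clinical variables "predict differential response and/or drop-out across treatment condition". Section III.E.1 makes no predictions for these analyses and names hierarchical multiple regression as the method, for "predicting response (i.e., 50% symptom reduction) and drop out for each treatment". On capacity it says "Based on the sample size estimate below" that "we will recruit a sample sufficient to include up to 24 predictors within these analyses", and it calls 24 a more than sufficient number. It gives no rule linking sample size to the number of predictors.

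The sample size estimate in Section III.E.2 concludes: "The total sample, then, will be N = 240, split equally between the two active treatments". It adds: "If needed, we propose oversampling by up to 40 participants to account for drop-outs from assessment or to bolster marginal effects". Section III gives the enrolled number as 280: "280 participants will be randomly assigned to receive ART, CPT or WL condition".

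Veteran/non-Veteran status is one of the predictors named in Section II.D. The footnote to Table 1.0 (Section III.C) states: "All civilian participants will be seen at the UC Health Stress Center". Site is not named as a term in the exploratory models.

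**The concern.** There are two separate problems. First, a subjects-per-predictor count is the wrong yardstick for a yes/no outcome. The information comes from the less frequent class, and fitting within one treatment halves the sample before that limit applies. If investigators rely on the stated capacity and enter anything near 24 predictors, apparent discrimination will be optimistic and the coefficients unstable.

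Second, the question is comparative: does a variable predict outcome differently under CPT than under ART? Section I makes this part of the study purpose, in asking whether some people respond better to one treatment. A model fitted in CPT participants and another in ART participants each describe one therapy. Neither estimates the difference between them or its uncertainty. That needs a predictor-by-treatment term or an equivalent formal comparison, and none is specified.

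A smaller matter concerns Veteran status. Because every civilian is at UC, every VA participant is a Veteran. Without site in the model, a difference between sites or their therapists can appear as a Veteran effect.

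**Working it through.** **Inputs.** N = 240 split equally, so 120 per treatment, and up to 40 more, so 280 or 140 per treatment (III.E.2). Up to 24 predictors; two yes/no outcomes; models for each treatment (III.E.1). Appendix C agrees with 120: it has 48 + 192 = 240 initial slots at 1:1:1, so 80 per arm. The 16 + 64 = 80 wait-list slots are re-randomised 1:1, giving 80 + 40 = 120 per therapy if every wait-list participant goes on to treatment. Response and drop-out rates are not given; 20% to 50% is assumed.

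**Reproducing 24.** Several routes lead to it:
- Ten subjects per predictor on the total: 240/10 = 24.
- Five subjects per predictor within one treatment: 120/5 = 24.
- The rule N ≥ 50 + 8m on the total comes close: (240 − 50)/8 = 23.75.

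The documents do not say which was used.

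**Events per predictor** = n × min(rate, 1 − rate) / 24.

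| Sample | 50% | 40% | 30% | 20% |
|---|---|---|---|---|
| One treatment, n = 120 | 60/24 = 2.5 | 48/24 = 2.0 | 36/24 = 1.5 | 24/24 = 1.0 |
| One treatment, n = 140 | 70/24 = 2.9 | 56/24 = 2.3 | 42/24 = 1.8 | 28/24 = 1.2 |
| Pooled, N = 240 | 120/24 = 5.0 | 96/24 = 4.0 | 72/24 = 3.0 | 48/24 = 2.0 |
| Pooled, N = 280 | 140/24 = 5.8 | 112/24 = 4.7 | 84/24 = 3.5 | 56/24 = 2.3 |

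The 50% column is a ceiling for any event rate and needs no assumption about rates. The other columns do.

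**A model that answers the question with all 24.** 24 predictors + treatment + 24 interactions = 49 terms. With N = 240 this gives 120/49 = 2.4 events per term at 50% and 48/49 = 1.0 at 20%.

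**Consequence, by simulation.** Logistic models were fitted to 24 pure-noise predictors, 500 runs per setting. At n = 120 the mean apparent AUC was 0.76 at a 50% rate and 0.82 at 20%, where the truth is 0.50. The nominal 5% overall test rejected in 12% and 16% of runs. At n = 240 the AUC was 0.68 and 0.72, and the overall test rejected in about 7%.

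**Veteran status and site.** Take UC as 48 of 240 slots (Appendix C), and assume 12 UC participants are Veterans. Civilians are then 36/240 = 0.15, and the Veteran-site correlation is (0.15 − 0.15 × 0.20)/√(0.15 × 0.85 × 0.20 × 0.80) = 0.84, a variance inflation of 1/(1 − 0.84²) = 3.4. With 24 UC Veterans the correlation is 0.67 and the inflation 1.8. With none, the two cannot be separated. The documents do not give the count.

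**The case against.** The strongest reply is that 24 is a ceiling and not a planned model, and that calling it more than sufficient may only mean that it exceeds what the investigators need. Section II.D names seven variables as examples. Seven predictors at n = 120 give 60/7 = 8.6 events each at 50% and 24/7 = 3.4 at an assumed 20%. This stands as a limit on how bad the analysis must be. It does not rescue the statement that the sample is sufficient for up to 24. Multiple regression may also be loose wording that covers logistic regression, and the analyses are the lowest tier of objective. Both are fair.

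Four stronger readings are tempting but not supported:

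- *That the investigators wrongly used the total sample.* No rule is stated, and 120/5 fits as well as 240/10. The shortage of events is the same either way.
- *That frequent false positives prove the sample too small.* With 24 independent tests at 5%, the chance of at least one is 1 − 0.95²⁴ = 71% at any sample size. In least-squares fits to noise it was about two thirds at n = 120 and 70% at n = 2,400, while the overall F test rejected in about 5%. That is multiplicity. The optimism in the logistic fits is what depends on sample size.
- *That a variable will be called a moderator when it is significant in one therapy and not the other.* The plan states no such rule. What can be said is that no interaction is specified.
- *That Veteran status is nearly aliased with site.* This holds only if few UC participants are Veterans. The Table 1.0 footnote allows Veterans at UC, and nothing excludes site as a predictor.

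**Conclusion.** The point holds. Within one treatment, 24 predictors cannot have more than 2.5 events each, or 2.9 with the full oversample, whatever the event rate. Even pooling all 280 gives at most 5.8. The claim of a sample sufficient for 24 is therefore unsupported on each reading examined. The figure of 1.0 rests on an assumed 20% rate. All these counts assume that every wait-list participant proceeds to treatment and that no outcome is missing; losses would lower them.

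The specified models also leave the question of differential prediction untested, because no predictor-by-treatment term or other formal comparison is named. The Veteran-site overlap is real in structure, but its size is unknown.

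This should be corrected, because who benefits from which therapy is part of the study's stated purpose. It does not touch the primary, secondary or tertiary analyses.

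**What to change.** For each binary outcome, replace the per-treatment regressions with one logistic model of CPT and ART participants together. Include treatment, site, baseline severity, and predictor-by-treatment interactions for a short pre-listed set. Base any statement about moderation on the interaction estimate and its interval.

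Set the number of terms from expected events and state the rule used. A fixed cap with several forced terms can leave no room. At an assumed 20% drop-out, 240 participants give 48 events, and ten events per term allows four terms. Treatment, site and baseline severity take three, and one moderator with its interaction needs two. Where events are this few, test moderators one at a time (five terms, 48/5 = 9.6 events each) or use penalised estimation.

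Delete the sentence on 24 predictors, or restate it with its rule and assumed event rates. State that the Veteran contrast can be separated from site only through Veterans treated at UC, and report their number.

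The cost is analysis wording only, with no new data. The price is fewer candidate predictors and a less favourable stated number.

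### Section III.E.2: the total of 706 does not follow from its printed inputs, and the claim that about 240 participants suffice for even small interaction effects has no stated scale to support it.

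*Combined protocol and SAP*

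**What the plan says.** Section III.E.2 of the combined protocol and SAP adopts Cohen's d as its metric for differences between treatments, with 0.2 as small, 0.5 as medium and 0.8 as large. It reports d = 0.16 for an earlier comparison of CPT with another active therapy. It then states that a similarly small difference (d below 0.2), at alpha 0.05, two-tailed, with power 0.80, "would require at least a total $N = 706$ ($n = 353$ for each active treatment"). It concludes that 240 would be too few for such a CPT-ART difference.

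For the interaction tests the section says "we estimate the necessary sample size to detect statistically significant Time x Treatment interactions across the entire power and ES range". It reports that "for the primary analysis we will have sufficient power to detect even small effects with a total sample size = 246" (123 per active treatment) and adds: "For the secondary analysis we will have sufficient power to detect even small effects with a total sample size = 138" (69 per active treatment). These calculations are described as ones "none of which include covariates". The section ends with "The total sample, then, will be N = 240, split equally between the two active treatments", and says that this estimate "is very conservative as it provides a sufficient sample size to detect even small interaction effects".

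Section III.E.1 gives the primary model three groups (CPT, ART, WL) and says the secondary analysis follows the same plan. It prints four time levels for the primary model but lists two, baseline and post-treatment. The preference analysis has two groups and four times. Appendix C randomises 1:1:1 at first and then re-randomises wait-list participants 1:1 to CPT or ART.

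**The concern.** The primary objective is CPT versus ART. Within a few lines the section says that 240 cannot detect a small difference between those arms and that 240 detects even small interaction effects. With two time points and randomised arms, the CPT-ART interaction contrast targets that same difference, so the two statements need a common scale. None is given: the interaction totals have no effect-size metric, correlation or power, and the only benchmark printed in the section is d.

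The section also never says what CPT-ART difference the trial can detect. A null CPT-ART result could then be read as having excluded a small difference. The total of 706, which is the section's own yardstick for a small effect, is too low for the inputs printed beside it.

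**Working it through.** **Step 1. The total of 706.** Inputs printed in III.E.2: alpha 0.05 two-sided, power 0.80, d below 0.2 (reported value 0.16), equal arms. The normal approximation is n per arm = 2(1.960 + 0.842)²/d².

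- d = 0.20: 2 × 7.849/0.0400 = 392.4. The exact two-sample t test needs 394 per arm, **788** in total.
- d = 0.16: 2 × 7.849/0.0256 = 613.2. The exact test needs 615 per arm, **1,230** in total.
- Inverting: 353 per arm has 80% power only at d of about 0.211, outside the printed range. Its exact power is 75.6% at d = 0.20 and 56.5% at d = 0.16.

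Any d below 0.2 needs more than 788, so calling 706 a minimum does not rescue it.

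**Step 2. The totals 246 and 138.** No inputs are printed. I used the standard within-between interaction test: λ = f²Nm/(1−ρ), df1 = (k−1)(m−1), df2 = (N−k)(m−1), for k groups and m times. Assumed inputs: f = 0.10, ρ = 0.5, alpha 0.05, 80% power, no covariates.

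- 3 groups × 2 times, N = 246: λ = 0.01 × 246 × 2/0.5 = 9.84, df 2 and 243, power 0.804. 246 is the smallest balanced total that reaches 80%.
- 2 groups × 4 times, N = 138: λ = 0.01 × 138 × 4/0.5 = 11.04, df 3 and 408, power 0.801. 138 is likewise the smallest.
- 3 × 2 with N = 240: power 0.793. With N = 280: power 0.855.
- 3 × 2 with N = 138: λ = 5.52, power 0.537.

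The match does not identify the inputs. For example, 2 × 2 with f = 0.11, ρ = 0.25 and 80% power also returns 246, and 3 × 2 with f = 0.20, ρ = 0.5 and 99% power also returns 138.

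**Step 3. What f = 0.10 means in SD units.** For two times, the change-score form is λ = N·s²/[2(1−ρ)], where s is the SD of the three arm means of change, in outcome SD units. Setting this equal to 2f²N/(1−ρ) gives s = 2f = 0.20.

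- WL at 0 and both therapies at D: s = D√2/3, so D = 0.424.
- Evenly spaced arms (0, D/2, D): s = D/√6, so D = 0.490.

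**Step 4. Omnibus power if small means D = 0.2 SD.** λ = Σnᵢ(meanᵢ − grand mean)²/residual, with residual 2(1−ρ) unadjusted or 1−ρ² with ANCOVA. Equal arms, equal SD at both times and no attrition are assumed. ρ is not in the documents. Each range runs from evenly spaced arms to the 0, D, D pattern.

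| ρ | Model | N = 240 | N = 280 |
|---|---|---|---|
| 0.5 | unadjusted | 19-24% | 21-27% |
| 0.5 | ANCOVA | 24-30% | 27-35% |
| 0.7 | ANCOVA | 33-43% | 38-49% |
| 0.9 | ANCOVA | 74-86% | 80-91% |

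With ANCOVA, 80% is reached at ρ of 0.884-0.914 (N = 240) or 0.863-0.899 (N = 280).

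**Step 5. Per-arm sizes.** At 1:1:1, 246/3 = 82 and 240/3 = 80. After the 80 wait-list participants are re-randomised 1:1, each therapy has 80 + 40 = 120 out of 240; on 246 the figure is 82 + 41 = 123.

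**Step 6. CPT-ART difference detectable at 80% power** (two-sample t test at post-treatment, two-sided 0.05).

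- 80 per arm: 0.446 SD. With ANCOVA, multiply by √(1−ρ²): 0.386 at ρ = 0.5, and 0.425 to 0.318 over ρ from 0.3 to 0.7.
- 120 per arm, pooled and treated as independent: 0.363 SD. With ANCOVA: about 0.31 at ρ = 0.5, and 0.346 to 0.259 over the same range.

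**The case against.** The plan has real defences. It openly says 240 is too few for a small CPT-ART difference, and correcting 706 changes no decision. It presents interactions as a separate calculation from the d-based comparisons. If f = 0.10 was the authors' small effect, power is adequate at 240 and 280. The section says of the comparisons with WL that "these ESs would be expected to be considerably larger than the CPT vs. PCT estimate", and a sample suited to differences of 0.4 to 0.5 SD fits that expectation. All of this stands.

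Four stronger readings are tempting, and the documents do not support them.

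- **That 246 is shown to be a three-arm total, or 138 to be the preference-analysis figure.** The inputs are inferred and other layouts return the same totals. Only the authors can settle it.
- **That 123 per active treatment is an arithmetic error.** It is a coherent count after wait-list re-randomisation and agrees with the equal split of 240. What is missing is the size of the arms in the randomised three-group comparison.
- **That the trial fails for small interactions as a matter of fact.** The low power in step 4 holds if small is read as d = 0.2, a benchmark the section gives for mean differences, and it depends on an assumed correlation. At ρ near 0.9 the claim would be roughly true.
- **That 280 contradicts 240.** The optional oversampling of up to 40 explains it.

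What remains is that a reader who has only the section's own benchmark cannot tell that small may mean nearly half an SD.

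**Conclusion.** The point holds in two parts, plus a clarification.

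First, 706 is wrong for its printed inputs: it should be 788 or 1,230, which reinforces the plan's own conclusion. This needs no outside assumption.

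Second, the assurance about even small effects, and the description of the estimate as very conservative, are unsupported as written. On the likeliest scale the detectable effect is 0.42-0.49 SD. On the section's printed scale, omnibus power stays below 50% for correlations up to 0.7, even with ANCOVA at 280. The secondary analysis shares the three-group plan, where 138 would give 54% power at f = 0.10 and ρ = 0.5. These figures rest on assumed inputs, equal SDs and no attrition.

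Third, the text should state that the randomised three-group comparison has 82 per arm at 246 and 80 at 240.

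A reader might infer that the sample is too small. That does not follow: the fault is in what the figures are said to mean.

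**What to change.** In section III.E.2:

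1. Replace 706 by 788 (394 per arm) for d = 0.20, or by 1,230 (615 per arm) for d = 0.16, and name the d used.
2. For 246 and 138, state the effect-size metric and value, correlation, alpha, power, and numbers of groups and times. Give the secondary analysis a figure for its own three-group layout. Reconcile the number of time points with III.E.1.
3. Print the per-arm size at initial randomisation beside the count after re-randomisation.
4. Replace the statements about even small effects and about being very conservative with the detectable difference in SD units.
5. State the CPT-ART difference detectable at 80% power: about 0.45 SD at 80 per arm, or about 0.36 SD at 120 per arm if re-randomised wait-list participants are pooled. Both are unadjusted; any smaller ANCOVA value should come with its assumed correlation and a range. Say which set the comparison uses.

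Cost: no added enrolment. The authors must retrieve their original inputs, and the stated detectable effects become less favourable. Item 5 is more than wording, because it commits the authors to an analysis set for CPT versus ART.
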